9.6 DATA MANAGEMENT

We will collect electronic patient records from the CPRD in the UK, Swedish NPR in Sweden, and SIDIAP in Spain. Routine procedures will include checking electronic files, maintaining security and data confidentiality, following analysis plans, and performing quality-control checks of all programmes. In Spain, SIDIAP will be in charge of the data management.

Each database custodian will maintain any patient-identifying information securely on site according to internal standard operating procedures. Evidera will maintain the data cuts according to internal procedures.

An Evidera data analyst will write and review programs to implement the analyses outlined in the *Data Analysis* section below. The project team will review all data outputs, including SAS[®] code as needed. Changes and corrections to programs stemming from the review will be made as appropriate. All programs will be saved, and the process documented. Security processes will be in place to ensure the safety of all systems and data. Every effort will be made to ensure that data are kept secure so that they cannot be accessed by anyone except select study staff.

Appropriate data storage and archiving procedures will be followed (i.e., storage on compact disk read-only memory [CD-ROM] or digital versatile disk [DVD]) with periodic backup of files to tape. Standard procedures will be in place at each research centre to restore files in the event of a hardware or software failure.

9.7 DATA ANALYSIS

Country-specific analyses will be conducted, and the heterogeneity of the results will be tested. If heterogeneity is not confirmed, then a pooled analysis will be conducted, and country effect will not be assessed.

9.7.1 PATIENT CHARACTERISTICS AND MEDICAL HISTORY

Patient characteristics at the IBS-C cohort entry date will be described for the full cohort of patients with IBS-C by reviewing data for a minimum of 12 months prior. Patient characteristics at the index date will be described for the cases and controls by reviewing data for a minimum of 12 months prior to index date.

The linaclotide PASS is a case-control study nested in a cohort of patients with IBS-C. The information of main interest from the databases (refer to Section 9.3.4 *Validation of the Diagnosis and Safety Endpoints*) will be validated for cases and controls through primary data collection from GPs in the UK and free-text review in Spain. If the validation results are satisfactory positive predictive value of EMRs in the UK and Spain $\geq 95\%$ and negative predictive value $\geq 99\%$, then information from the whole cohort would be used to estimate the incidence of diarrhoea and the incidence of SCD in the cohort of IBS-C patients and the relative risks of SCD and the exposures of interest (mainly linaclotide) as detailed below in Section 9.7.2 *Cohort analyses*. Otherwise, only ORs of SCD and the same exposures of interest will be estimated using data from cases and controls as detailed below in Section 9.7.3 *Nested Case-control Analyses*.

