4.3 RESEARCH QUESTION AND OBJECTIVES

The specific research questions and objectives for this study are to:

- Estimate the risk (case-control odds ratio [OR]) of SCD (case) among patients with IBS-C (source population) who received linaclotide prescriptions vs those who did not, controlling for other potential SCD risk factors (socio-demographics, comorbidities [up to 15], co-medications [up to 15] and other potential variables of interest [up to 10])
- Investigate potential risk factors associated to SCD in patients with IBS-C
- Describe the crude incidence of diarrhoea among patients with IBS-C

If allowed by the results of the cases and controls validation as discussed below, two additional objectives will be addressed:

- Describe the crude incidence of SCD among patients with IBS-C (source population) prescribed linaclotide (first-time users)

- Describe the crude incidence of SCD among patients with IBS-C (source population) prescribed linaclotide (first-time users) who are at increased risk of SCD:
 - Patients ≥ 65 years
 - Patients with hypertension, diabetes, or cardiovascular disease diagnostic codes

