Using the latest available information, the sample size across the three countries is approximately 329,000 patients with IBS-C or potential IBS-C, with an exposure to linaclotide rate ranging from 1% to 4%. If the results of the validation of cases are satisfactory with positive predictive value of SCD algorithms in the UK and Spain $\geq 95\%$, information from the whole cohort will be used to estimate risk of developing SCD across the groups of patients with or without linaclotide exposure, under a cohort study design. If the positive predictive values are $< 95\%$, a case-control analysis will be performed. Assuming the percentage of patients exposed to linaclotide among controls is around 1%, a minimum of 401 case-control pairs would be required to detect an $OR \geq 4$ and 745 possible case-control pairs to detect an $OR \geq 3$ with 80% power, under a matched case-control study design. Within the total IBS-C cohort, it is expected to accrue approximately 11,800 algorithm-identified, potential SCD cases. The final number of case-control pairs to be included in the analyses will depend on the performance of SCD algorithms and case validation results and is expected to be sufficient to detect an $OR \geq 3$ at 80% power, given the number of potential SCD cases identified by the algorithms.

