4.9 DATA ANALYSES

Country-specific analyses will be conducted, and the heterogeneity of the results will be tested. If heterogeneity is not confirmed, then a pooled analysis aggregating data for all three countries will be conducted and country effect will not be assessed.

Patient characteristics at cohort entry date will be described for the full cohort of patients with IBS-C, as well as incidence rate of diarrhoea.

If the results of the validation of cases are satisfactory positive predictive value of EMRs in the UK and Spain $\geq 95\%$ and negative predictive value $\geq 99\%$, then information from the whole cohort will be used to estimate incidence and incidence density rates for those groups of patients with IBS-C prescribed linaclotide and those who are potentially at increased risk of SCD and prescribed linaclotide. The crude incidence of diarrhoea and of severe complications of diarrhoea will be described by calculating the proportion of patients with IBS-C experiencing diarrhoea and SCD, respectively, and their associated 95% confidence intervals (CIs). Crude incidence density rates of SCD will be also calculated.

Additionally, the hazard ratios of SCD and the exposures of interest (mainly prescription of linaclotide) will be estimated using Cox proportional hazard models. ORs of SCD and the same exposures of interest will be estimated using data from cases and matched controls by applying conditional logistic regression analysis.

If the results of the validation of cases in the UK and Spain are not satisfactory (positive predictive value of our outcome algorithm in the UK and Spain $< 95\%$ or negative predictive value $< 99\%$), only the nested case-control study will be performed and ORs of SCD and the same exposures of interest will be estimated using data from cases and matched controls by applying conditional logistic regression analysis.

The goal is to assess SCD among patients who were treated with linaclotide, were ≥ 65 years old, and had history of hypertension, diabetes or cardiovascular disease diagnostic codes (i.e., SCD occurrence is the outcome variable [yes/no]. and the independent variables of main interest are whether the patient has a prescription for linaclotide, a prescription for laxatives, the patient is ≥ 65 years old, and the patient has hypertension, diabetes, or cardiovascular disease diagnostic codes, all of them at index date, or not, controlling for potential confounders).

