8 RESEARCH QUESTIONS AND OBJECTIVES

8.1 RESEARCH QUESTIONS

The study will address the following research questions:

- What are the risk factors associated with SCD in patients with IBS-C (specifically linaclotide prescription vs no linaclotide prescription)?
- What is the estimated risk of SCD among IBS-C patients prescribed linaclotide (if allowed by the results of the cases and controls validation as discussed below)?

Both research questions will be assessed in three different countries: the UK, Sweden and Spain

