9.3.4 VALIDATION OF THE DIAGNOSIS AND SAFETY ENDPOINTS

Information on IBS-C is not well-captured by standard diagnosis codes. SCD is also not coded as such in the databases. Therefore, IBS-C and SCD will be validated by the physicians treating the patients selected as cases or as controls. This will require additional primary data collection from GPs that is possible in the UK with the use of CPRD.

The process in the UK would consist of asking cases' attending GPs to confirm the type of IBS. All cases (patients with IBS-C experiencing SCD) will be characterised in further detail through contact with their PCPs. A questionnaire will be mailed to the GP with whom each identified subject is registered to validate both diagnoses (IBS and SCD [if applicable]; please refer to [Annex 3](#)).

The feasibility of using this questionnaire to collect validation information about cases was evaluated through a pilot study with a small number of physicians in the UK. This UK pilot study targeted a group of 25 PCPs to test the questionnaire and contribute to its development. The section, *Pilot Study Summary Report*, in Annex 3 reports on the pilot study conduct. This pilot study included additional questions to PCPs about preferred codes or code combinations used to record diagnoses of patients with IBS-C.

Although it was originally planned for the validation study to also be undertaken in Spain using GP questionnaires, since 2018, SIDIAP no longer allows the possibility to contact physicians for extracting extended additional information on the patient through long- questionnaires. However, there is the possibility of a text review of the primary care records. This text review can be used to validate cases of interest, conducted by IDIAP's clinical researchers. For this study, it is recommended by the data custodians that a review of free-text in the patient's medical records is conducted to improve the validity of the actual study, in place of the previously planned validation strategy using questionnaires to GPs. This free-text review is made after an anonymisation process of the clinical records and a natural language processing of the text.

We will validate our outcome identification algorithm by calculating the positive predictive value and the negative predictive value in both countries.

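### The validation gate is worded inconsistently and works all-or-nothing: a shortfall in PPV alone removes the SCD incidence in linaclotide users, while a pass lets through an uncorrected figure that can be about 18% too low

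*Protocol*

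**What the plan says.** **The gate.** Sections 4.9, 9.5.1, 9.7.1 and 9.7.2.2 require both PPV of at least 95% and NPV of at least 99% before the whole cohort is used for SCD. Section 4.9 gives the failure rule as "or negative predictive value $< 99\%$), only the nested case-control study will be performed", and 9.7.1 gives its consequence as "Otherwise, only ORs of SCD and the same exposures of interest will be estimated using data from cases and controls". Section 4.8 attaches its statement that "information from the whole cohort will be used to estimate risk of developing SCD" to the PPV limit alone.

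**What depends on it.** Section 4.3 introduces SCD incidence in first-time linaclotide users, and in those at increased risk, with "If allowed by the results of the cases and controls validation as discussed below, two additional objectives will be addressed". Section 8.1 words the research question in the same way: "What is the estimated risk of SCD among IBS-C patients prescribed linaclotide (if allowed by the results of the cases and controls validation". The incidence of diarrhoea carries no such condition in 4.3 or 8.2, and 4.9 first describes it for the full cohort. Sections 9.5.1 and 9.7.1 nevertheless put it behind the gate.

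**Validation.** Section 9.3.4 says that UK cases "will be characterised in further detail through contact with their PCPs", and that PPV and NPV will be calculated in the UK and Spain. Section 9.2.1.4 says there is no validation in Sweden. No section uses the estimated PPV or NPV to correct an incidence. Unvalidated events are handled by scenario analyses, in the case-control part only (9.7.3.1).

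**The concern.** There are two problems.

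First, the versions of the gate lead to different analyses. With PPV 96% and NPV 98%, section 4.8 would run the cohort analysis and section 4.9 would forbid it. On one reading diarrhoea incidence is always reported, and on the other it disappears when the SCD algorithm fails.

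Second, the rule treats validation as a switch. On one side an uncorrected incidence is published as if the algorithm were exact. On the other side there is no absolute risk at all, only odds ratios. The document derives neither threshold. At stake is the absolute risk of SCD in linaclotide users, which an odds ratio does not give.

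**Working it through.** **Inputs from the protocol.** Section 4.8: about 329,000 patients, linaclotide exposure of 1% to 4%, and the statement that "it is expected to accrue approximately 11,800 algorithm-identified, potential SCD cases". Section 9.5.2: around 2,000 exposed patients in CPRD. Section 9.5: a forecast 47% of exposed patients in Sweden (an older projection).

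**Assumptions, not in the protocol.** The PPV and NPV values tried, the number of validated cases, and algorithm cases being as frequent in linaclotide users as in the whole cohort. Person-time is not given, so proportions stand in for rates.

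**The plan's own figures.** The gate has no calculation to reproduce. The pair counts for the design left after a failure do reproduce. With P = OR/(1+OR), the number of pairs is [(1.96/2 + 0.8416√(P(1−P)))² / (P−0.5)²] / [p0(1−p1) + p1(1−p0)]. At p0 = 1% this gives 19.26/0.04806 = 401 for OR 4 and 28.92/0.03882 = 745 for OR 3, as in section 4.8. The case-control sizing is not in question here.

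**Step 1: does the gate track accuracy?** True cases = 11,800 × PPV + 317,200 × (1 − NPV), where 317,200 = 329,000 − 11,800.

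| PPV | NPV | Gate | True cases | Uncorrected 11,800 is |
|---|---|---|---|---|
| 95% | 99% | passes | 11,210 + 3,172 = 14,382 | 18% too low |
| 95% | 99.9% | passes | 11,210 + 317 = 11,527 | 2% too high |
| 94% | 99.9% | fails | 11,092 + 317 = 11,409 | 3% too high |
| 95% | 98% | passes in 4.8, fails in 4.9 | 11,210 + 6,344 = 17,554 | 33% too low |

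The third row is nearer the truth than the first, yet only the first is reported. The fourth shows what omitting NPV in 4.8 can cost.

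**Step 2: what a PPV correction gives.** The crude algorithm incidence is 11,800/329,000 = 3.59%. At PPV 80% the corrected value is 3.59% × 0.80 = 2.87%. Relative SE = √[1/N + (1−PPV)/(PPV × v)], with N algorithm cases in users and v of them validated. All rows use PPV 80%.

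| N | Basis | v | Relative SE | 95% interval |
|---|---|---|---|---|
| 118 | 1% of 11,800, three countries | 100 | √(0.00847 + 0.0025) = 0.105 | ±21% |
| 472 | 4% of 11,800, three countries | 100 | √(0.00212 + 0.0025) = 0.068 | ±13% |
| 63 | 118 × (1 − 0.47), UK and Spain | 50 | √(0.01587 + 0.005) = 0.144 | ±28% |
| 63 | same | 15 | √(0.01587 + 0.01667) = 0.180 | ±35% |
| 72 | 2,000 × 3.59%, UK alone | 50 | √(0.01389 + 0.005) = 0.137 | ±27% |
| 72 | same | 15 | √(0.01389 + 0.01667) = 0.175 | ±34% |

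**Step 3: what a PPV correction does not give.** It removes false positives only. At PPV 80% and NPV 99%, true positives are 9,440 of 9,440 + 3,172 = 12,612 true cases, or 75%. At NPV 98% they are 9,440 of 15,784, or 60%.

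**The case against.** **NPV is a genuine reason for caution.** A reader might infer that incidence is withheld for no statistical reason. The documents do not support that. Four sections include an NPV condition, and confirming algorithm-positive patients cannot recover missed cases. An unlabelled PPV-corrected figure would understate absolute risk in a safety study. This stands, and it is why the estimate must be called a lower bound. It does not justify silence when only PPV fails, since the gate itself accepts 3,172 missed cases (27% of 11,800) without correction.

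**Validation does not supply a complete confirmed numerator.** The all-cases wording in 9.3.4 may suggest that it does. But Sweden has no validation, Annex 3 twice allows for only a sample, section 4.10 reports a very low earlier UK response, and 9.7.3.1 expects events that are never validated. What validation supplies is an estimated PPV. Using it assumes that returned cases represent the rest. This stands.

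**The condition is declared.** It would be tempting to say that a research question is left unanswered in contradiction of the objectives. Although the summary at the front of the protocol lists the question without a condition, sections 4.3, 8.1 and 8.2 state it openly. Dropping SCD incidence is therefore a declared consequence, not a contradiction. The contradiction concerns the NPV arm and diarrhoea incidence.

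**Detail may belong in the SAP.** The interval method, and whether the gate is judged on a point estimate, may fairly be settled there, so no fault is claimed on those. The all-or-nothing rule and its conflicting wordings are fixed in the protocol itself.

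**Conclusion.** The concern holds in a limited form. The gate is worded in two incompatible ways, wrongly captures diarrhoea incidence, and separates reporting from non-reporting without tracking accuracy. At exactly PPV 95% and NPV 99% it passes a count about 18% too low; at PPV 94% and NPV 99.9% it suppresses one about 3% too high. These are illustrations at chosen values, and the direction of error depends mainly on NPV.

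A PPV below 95% does not by itself make incidence in linaclotide users inestimable. At an assumed PPV of 80%, a corrected estimate has an interval of about ±13% to ±21% with 118 to 472 exposed algorithm cases and 100 validated. Those counts include Sweden, where no PPV is available. With 63 to 72 UK or UK-and-Spain cases and 15 to 50 validated, the range is about ±27% to ±35%. High-risk subgroups would be less precise. The result rests on representative validation returns and on a denominator that, in section 4.8, includes potential IBS-C.

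**What to change.** 1. Use one gate wording, with both PPV and NPV, in 4.8, 4.9, 9.5.1 and 9.7. Confine it to the uncorrected whole-cohort SCD incidence and the Cox analyses.
2. Remove diarrhoea incidence from the gate in 9.5.1 and 9.7.1.
3. Whatever the gate result, report SCD incidence in linaclotide users for the UK and Spain only, as algorithm-positive count × PPV / person-time. Preferably use the PPV found in linaclotide users. The interval should combine the error in the count and in the PPV.
4. Label that estimate a lower bound, or add an NPV-corrected version as a sensitivity analysis. The latter will be sensitive: moving NPV from 99.9% to 99% raises missed cases from 317 to 3,172.
5. State the validation response rate and the assumption that validated cases represent the rest.
6. Treat the high-risk subgroups in the same way, but as exploratory, because PPV may differ there.

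The cost is a text change, including the conditional wording in 4.3, 8.1 and 8.2, and a short calculation on data already planned. The price is wider intervals and reliance on representative returns.

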9.7.2 COHORT ANALYSES

9.7.2.1 CRUDE INCIDENCE OF DIARRHOEA AND CRUDE INCIDENCE OF SEVERE COMPLICATIONS OF DIARRHOEA

Exposure to linaclotide and other risk factors (e.g., laxatives) will be ascertained from the prescription information recorded in the databases. Person-time at risk (person-years and person-weeks) for developing complications of diarrhoea will be used to compute the incidence and incidence density rates among patients in the IBS-C cohort.

Crude incidence density rates (person-time incidence rates) for the full cohort of patients with IBS-C will be graphically displayed over the follow-up period since cohort entry date, to ascertain if rates are homogeneous over time. Crude incidence density rates for sub-cohorts, defined by exposure to potential risk factors for experiencing SCD (e.g., current users of linaclotide), will also be graphically displayed over time since the first treatment prescription. These figures will guide whether the follow-up periods should be broken into several intervals with different incidence density rates of diarrhoea complications (based on the clinical development programme of linaclotide, diarrhoea has been observed to be more frequent early in treatment) or not. Additionally, the first six months after linaclotide launch will be studied separately, since patients with prevalent IBS-C who are exposed to linaclotide during this period

could have more severe cases of IBS-C, have exhausted other treatment options, and have a different risk profile than incident patients with IBS-C.

The crude incidence of diarrhoea and the crude incidence of SCD in the full cohort of patients with IBS-C will be described by calculating the proportion of patients experiencing at least one episode of diarrhoea and the proportion of patients experiencing at least one episode of SCD, as well as their corresponding 95% CIs. The crude incidences of diarrhoea and of SCD in the sub-cohorts of patients with prescriptions of linaclotide will be described by calculating the proportions of patients experiencing diarrhoea or experiencing SCD, respectively, among those at risk for each of the time intervals (as determined graphically) since first treatment prescription, as well as the corresponding 95% CIs. Crude incidence density rates (person-time incidence rates) will also be computed with their corresponding 95% CIs. The incidence of SCD will be assessed separately for death subsequent to diarrhoea (≤ 45 days after diarrhoea diagnosis date) due to the seriousness of this complication (deadly SCD).

All incidence and incidence density rates will also be calculated separately for those groups of patients with increased risk of SCD as defined in the objectives: patients ≥ 65 years and patients with hypertension, diabetes, or cardiovascular disease diagnostic codes.

